5.2 Exclusion Criteria

The participant must be excluded from the study if the participant:

Medical Conditions

1. Is a WOCBP who has a positive highly sensitive pregnancy test within 24 hours for urine or 72 hours for serum prior to randomization or treatment allocation (see Appendix 5). If the urine test is positive or cannot be confirmed as negative, a serum pregnancy test will be required.

Note: If 24 hours for urine or 72 hours for serum have elapsed between the screening pregnancy test and the first dose of study intervention, another pregnancy test (urine or serum) must be performed and must be negative in order for participant to start receiving study medication.

Prior/Concomitant Therapy

- 2. Has received prior therapy with an anti-PD-1, anti-PD-L1, or anti-PD-L2 agent or with an agent directed to another stimulatory or coinhibitory T-cell receptor (eg, CTLA-4, OX-40, CD137).
- 3. Has received prior radiotherapy to the thorax, including radiotherapy to the esophagus, mediastinum, or breast. Participants receiving radiotherapy to the contralateral breast at least 5 years prior to randomization may still be eligible.
- 4. Has received a live vaccine within 30 days prior to the first dose of study intervention. Examples of live vaccines include, but are not limited to, the following: measles, mumps, rubella, varicella/zoster (chicken pox), yellow fever, rabies, *Bacillus* Calmette–Guérin (BCG), and typhoid vaccine. Seasonal influenza vaccines for injection are generally killed virus vaccines and are allowed; however, intranasal influenza vaccines (eg, FluMist[®]) are live attenuated vaccines and are not allowed. Refer to Section 6.5 for information on COVID-19 vaccine.

Prior/Concurrent Clinical Study Experience

5. Has received an investigational agent or has used an investigational device within 4 weeks prior to the first dose of study intervention administration.

Diagnostic Assessments

- 6. Has a diagnosis of immunodeficiency or is receiving chronic systemic steroid therapy (in dosing exceeding 10 mg daily of prednisone equivalent) or any other form of immunosuppressive therapy within 7 days prior the first dose of study drug.
- 7. Has a known additional malignancy that is progressing or has required active treatment within the past 3 years. A prior NSCLC that occurred and was treated curatively at least 2 years prior to the date of the current diagnosis would be considered a separate primary lung cancer, and therefore an additional malignancy.

Note: Participants with basal cell carcinoma of the skin, squamous cell carcinoma of the skin, or carcinoma in situ (eg, breast carcinoma, cervical cancer in situ) that have undergone potentially curative therapy are not excluded.

- 8. Has a known hypersensitivity (≥Grade 3) to pembrolizumab and/or any of its excipients.
- 9. Has a history of (non-infectious) pneumonitis that required steroids or has current pneumonitis.
- 10. Has a known history of hepatitis B (defined as hepatitis B surface antigen [HBsAg] reactive) or known active hepatitis C virus (defined as HCV RNA [qualitative] is detected) infection.

Note: No testing for hepatitis B and hepatitis C is required unless mandated by local health authority.

- 11. Has an active autoimmune disease that has required systemic treatment in past 2 years except replacement therapy (eg, thyroxine, insulin, or physiologic corticosteroid).
- 12. Has an active infection requiring systemic therapy.
- 13. Has a known history of human immunodeficiency virus (HIV) infection. No HIV testing is required unless mandated by local health authority.
- 14. Has a known history of active tuberculosis (TB; *Bacillus* tuberculosis). No TB testing is required unless mandated by local health authority.
- 15. Has a history or current evidence of any condition, therapy, or laboratory abnormality that might confound the results of the study, interfere with the participant's participation for the full duration of the study, or is not in the best interest of the participant to participate, in the opinion of the treating investigator.
- 16. Has a known psychiatric or substance abuse disorder that would interfere with the participant's ability to cooperate with the requirements of the study.

Other Exclusions

- 17. Is pregnant or breastfeeding or expecting to conceive or father children within the projected duration of the study, starting with the Screening Visit through 120 days after last dose of pembrolizumab/placebo and 180 days after the last radiotherapy dose.
- 18. Has had an allogeneic tissue/solid organ transplant.
- 19. Participants who have not adequately recovered from major surgery or have ongoing surgical complications.

Note: Country-specific differences are noted in Appendix 7.

5.3 Lifestyle Considerations

5.3.1 Meals and Dietary Restrictions

Participants should maintain a normal diet unless modifications are required to manage an AE such as diarrhea, nausea, or vomiting.

5.3.2 Caffeine, Alcohol, and Tobacco Restrictions

Participants should maintain a normal lifestyle; however, may be encouraged to restrict tobacco use on the study.

5.4 Screen Failures

Screen failures are defined as participants who consent to participate in the clinical study, but are not subsequently randomized in the study. A minimal set of screen-failure information is required to ensure transparent reporting of screen-failure participants to meet the CONSORT publishing requirements and to respond to queries from regulatory authorities. Minimal information includes demography, screen-failure details, eligibility criteria, and any AEs or SAEs meeting reporting requirements as outlined in the data entry guidelines.

5.5 Participant Replacement Strategy

A participant who discontinues from study intervention or withdraws from the study will not be replaced.

6 STUDY INTERVENTION

Study intervention is defined as any investigational intervention(s), marketed product(s), placebo, or medical device(s) intended to be administered to a study participant according to the study protocol.

6.1 Study Intervention(s) Administered

In alignment with the study update memo sent to Investigators on 29-AUG-2024, all study participants must stop ongoing treatment with pembrolizumab/placebo. These participants must complete EOT visit followed by Safety Follow-up visit per protocol. All remaining study participants who have completed the safety reporting windows for AEs and SAEs per protocol must be discontinued from the study. All study participants will undergo unblinding at the end of the study. Investigators may apply for unblinding participants per protocol in the interim.

The study interventions to be used in this study are outlined in Table 3.

Country-specific differences are noted in Appendix 7.

Arm Name	Arm Type	Intervention Name	Intervention Type	Dose Formula-	Unit Dose Strength(s)	Dosage Level(s)	Route of Administ	Regimen/ Treatment	Use	IMP or NIMP/A	Sour- cing
Arm 1	Experimental	Pembrolizumab (MK-3475)	Drug	Injection, Solution	25 mg/mL	200 mg	IV Infusion	Q3W x17 cycles (~1 year)	Test Product	IMP	Central
Arm 1	Experimental	SBRT	Radiation	Not Applicable	Peripheral Tumors: 45-60 Gy in 3 fractions (preferred); 48-50 Gy in 4 fractions (acceptable); 50-55 Gy in 5 fractions (acceptable) Abutting the chest wall: 48-50 Gy in 4 fractions; 50-55 Gy in 5 fractions Central Tumors: 50-55 Gy in 5 fractions; 60-70 Gy in 8 fractions	Peripheral Tumors: 45-60 Gy in 3 fractions (preferred); 48 50 Gy in 4 fractions (acceptable); 50 55 Gy in 5 fractions (acceptable) Abutting the chest wall: 48 50 Gy in 4 fractions; 50 55 Gy in 5 fractions Central Tumors: 50-55 Gy in 5 fractions; 60 70 Gy in 8 fractions	External Beam Radiation	~Q3D over 2 weeks	Background Treatment	NIMP/A xMP	Local
Arm 2	Placebo Comparator	Placebo	Drug	Injection, Solution	N/A	N/A	IV Infusion	Q3W × 17 cycles (~1 year)	Placebo	IMP	Local

Table 3Study Interventions

Arm	Arm Type	Intervention	Intervention	Dose	Unit Dose	Dosage Level(s)	Route of	Regimen/	Use	IMP or	Sour-
Name		Name	Туре	Formula-	Strength(s)		Administ	Treatment		NIMP/A	cing
				tion			ration	Period		xMP	-
Arm 2	Active Comparator	SBRT	Radiation	tion Not Applicable	Peripheral Tumors: 45-60 Gy in 3 fractions (preferred); 48-50 Gy in 4 fractions (acceptable); 50-55 Gy in 5 fractions (acceptable) Abutting the chest wall: 48-50 Gy in 4 fractions; 50-55 Gy in 5 fractions Central Tumors: 50-55 Gy in 5 fractions;	Peripheral Tumors: 45-60 Gy in 3 fractions (preferred); 48 50 Gy in 4 fractions (acceptable); 50 55 Gy in 5 fractions (acceptable) Abutting the chest wall: 48 50 Gy in 4 fractions; 50 55 Gy in 5 fractions Central Tumors: 50-55 Gy in 5 fractions; 60 70 Gy in 8 fractions	ration External Beam Radiation	Period ~Q3D over 2 weeks	Background Treatment	xMP NIMP/A xMP	Local
					60-70 Gy in 8 fractions						

EEA=European Economic Area; IMP=investigational medicinal product; IV=intravenous, N/A=not applicable; NIMP/AxMP=noninvestigational/auxiliary medicinal product.Q3W=every 3 weeks; SBRT=stereotactic body radiotherapy

The classification of IMP and NIMP/AxMP in this table is based on guidance issued by the European Commission and applies to countries in the EEA. Country differences with respect to the definition/classification of IMP and NIMP/AxMP may exist. In these circumstances, local legislation is followed.

56

All study interventions will be administered on an outpatient basis.

All products indicated in Table 3 will be provided centrally by the Sponsor or locally by the study site, subsidiary, or designee, depending on local country operational or regulatory requirements.

For any commercially available product that is provided by the study site, subsidiary, or designee, every attempt will be made to source these supplies from a single lot/batch number. The study site is responsible for recording the lot number, manufacturer, and expiry date for any locally purchased product as per local guidelines unless otherwise instructed by the Sponsor.

Refer to Section 8.1.8 for details regarding administration of the study intervention.

6.2 Preparation/Handling/Storage/Accountability

6.2.1 Dose Preparation

Details on preparation and administration of pembrolizumab and placebo are provided in the Pharmacy Manual.

6.2.2 Handling, Storage, and Accountability

The investigator or designee must confirm appropriate temperature conditions have been maintained during transit for all study intervention received, and any discrepancies are reported and resolved before use of the study intervention.

Only participants enrolled in the study may receive study intervention, and only authorized site staff may supply or administer study intervention. All study interventions must be stored in a secure, environmentally controlled, and monitored (manual or automated) area in accordance with the labeled storage conditions with access limited to the investigator and authorized site staff.

The investigator, institution, or the head of the medical institution (where applicable) is responsible for study intervention accountability, reconciliation, and record maintenance (ie, receipt, reconciliation, and final disposition records).

For all study sites, the local country Sponsor personnel or designee will provide appropriate documentation that must be completed for drug accountability and return, or local discard and destruction if appropriate. Where local discard and destruction is appropriate, the investigator is responsible for ensuring that a local discard/destruction procedure is documented.

The study site is responsible for recording the lot number, manufacturer, and expiry date for any locally purchased product (if applicable) as per local guidelines unless otherwise instructed by the Sponsor.

57

The investigator shall take responsibility for and shall take all steps to maintain appropriate records and ensure appropriate supply, storage, handling, distribution, and usage of study interventions in accordance with the protocol and any applicable laws and regulations.

6.3 Measures to Minimize Bias: Randomization and Blinding

6.3.1 Intervention Assignment

Intervention allocation/randomization will occur centrally using an IRT system. There are 2 study intervention arms. Participants will be assigned randomly in a 1:1 ratio to pembrolizumab with SBRT or placebo with SBRT, respectively.

6.3.2 Stratification

Intervention allocation/randomization will be stratified according to the following factors:

- Disease stage: Stage I versus Stage II
- ECOG performance status: 0 or 1 versus 2
- Geographic region of enrollment site: East Asia versus non-East Asia
- Reason for not receiving surgery: medically inoperable versus refused surgery

6.3.3 Blinding

In alignment with the study update memo sent to Investigators on 29-AUG-2024, all study participants must stop ongoing treatment with pembrolizumab/placebo. These participants must complete EOT visit followed by Safety Follow-up visit per protocol. All remaining study participants who have completed the safety reporting windows for AEs and SAEs per protocol must be discontinued from the study. All study participants will undergo unblinding at the end of the study. Investigators may apply for unblinding participants per protocol in the interim.

The subsection below is retained for reference.

A double-blinding technique will be used. Pembrolizumab and placebo (normal saline) will be prepared and/or dispensed in a blinded fashion by an unblinded pharmacist or qualified study-site personnel. The participant, the investigator, and Sponsor personnel or delegate(s) who are involved in the study intervention administration or clinical evaluation of the participants are unaware of the intervention assignments.

6.4 Study Intervention Compliance

If there are interruptions in the study intervention schedule or infusion/injection was stopped, the details of and reason for any interruption or infusion/injection cessation of study intervention will be documented in the participant's medical record.

Interruptions from the protocol-specified treatment >12 weeks require consultation between the investigator and the Sponsor and written documentation of the collaborative decision on participant management.

6.5 Concomitant Therapy

Medications or vaccinations specifically prohibited in the exclusion criteria are not allowed during the ongoing study. If there is a clinical indication for any medication or vaccination specifically prohibited, discontinuation from study therapy or vaccination may be required. the investigator should discuss any questions regarding this with the Sponsor's Clinical Director. The final decision on any supportive therapy or vaccination rests with the investigator and/or the participant's primary physician. However, the decision to continue the participant on study intervention requires the mutual agreement of the investigator, the Sponsor, and the participant.

Participants are prohibited from receiving the following concomitant therapy or vaccination during the course of the study:

- Antineoplastic systemic chemotherapy or biological therapy
- Immunotherapy not specified in this protocol
- Investigational agents other than pembrolizumab
- Radiation therapy not specified in this protocol
- Live or liveattenuated vaccines within 30 days prior to the first dose of study intervention and while participating in the study. Examples of live vaccines include, but are not limited to, the following: measles, mumps, rubella, varicella/zoster, yellow fever, rabies, BCG, and typhoid vaccine. Seasonal influenza vaccines for injection are generally killed virus vaccines and are allowed; however, intranasal influenza vaccines (eg, FluMist®) are live attenuated vaccines and are not allowed.
- Note: Any licensed COVID-19 vaccine (including for Emergency Use) in a particular country is allowed in the study as long as they are mRNA vaccines, replication-incompetent adenoviral vaccines, or inactivated vaccines. These vaccines will be treated just as any other concomitant therapy.

Investigational vaccines (ie, those not licensed or approved for Emergency Use) are not allowed.

- Systemic glucocorticoids except when used for the following purposes:
 - To modulate symptoms of an AE that is suspected to have an immunologic etiology
 - For the prevention of emesis
 - To premedicate for IV contrast allergies
 - To treat asthma or chronic obstructive pulmonary disease (COPD) exacerbations (only short-term oral or IV use in doses >10 mg/day prednisone equivalent)
 - For chronic systemic replacement not to exceed 10 mg/day prednisone equivalent

- Treatment of radiation pneumonitis. Refer to Table 4 to follow the same management guidelines for irAE pneumonitis
- Other glucocorticoid use except when used for the following purposes:
 - For topical use or ocular use
 - Intraarticular joint use
 - For inhalation in the management of asthma or COPD

Participants who, in the assessment of the investigator, require the use of any of the aforementioned treatments for clinical management should be removed from the study.

All treatments that the investigator considers necessary for a participant's welfare may be administered at the discretion of the investigator in keeping with the community standards of medical care. All concomitant medication will be recorded on the eCRF including all prescription, over-the-counter (OTC) products, herbal supplements, and IV medications and fluids. If changes occur during the study period, documentation of drug dosage, frequency, route, and date should also be included on the eCRF.

All concomitant medications received within 42 days prior to the first dose of study intervention and up to 30 days after the last dose of study intervention should be recorded. Concomitant medications administered 30 days after the last dose of study intervention should be recorded for SAEs and events of clinical interest (ECIs) as defined in Section 8.4.7.

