Treatment with pembrolizumab or placebo control will continue until 17 cycles have been administered (approximately one year), or until disease recurrence, unacceptable adverse events, intercurrent illness that prevents further administration of treatment, death from any cause, investigator decision, or participant decision or withdrawal of consent, whichever occurs first.

Participants who discontinue for reasons other than disease recurrence, or where radiographic disease recurrence has not been verified by BICR, will have posttreatment follow-up imaging until disease recurrence is documented radiographically and verified by BICR, withdrawing consent, pregnancy, death, loss to follow-up or early study termination, whichever occurs first. Images will continue to be obtained even after initiating the new anticancer therapy if recurrence has not been documented or verified by BICR.

After the end-of-treatment, each participant will be followed for the occurrence of AEs and spontaneously reported pregnancy as described in Section 8.4.

All participants will be followed by telephone for OS until death, withdrawal of consent, or the end of the study.

Specific procedures to be performed during the study, including prescribed times and associated visit windows, are outlined in Section 1.3, Table 1 of the SoA. Details of each procedure are provided in Section 8.

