7 DISCONTINUATION OF STUDY INTERVENTION AND PARTICIPANT WITHDRAWAL

7.1 Discontinuation of Study Intervention

NOTE: Based on the data from an interim safety and efficacy analysis for KEYNOTE¬867 (data cutoff 11-JUN-2024), the eDMC recommended stopping the study since pembrolizumab in combination with SBRT did not demonstrate an improvement in EFS or OS, the study's primary endpoint and key secondary endpoint, respectively, compared to placebo plus SBRT, and the benefit/risk profile of the combination did not support continuing the trial. All prespecified interim analyses after IA1 and final analysis of the study described in the SAP will not be performed. Safety analysis will be performed at the end of the study; there will be no further pre-planned analyses for efficacy and ePRO endpoints collected from participants beyond the IA1 cutoff date of 11-JUN-2024. The subsections below are retained for reference.

Discontinuation of study intervention does not represent withdrawal from the study.

As certain data on clinical events beyond study intervention discontinuation may be important to the study, they must be collected through the participant's last scheduled followup, even if the participant has discontinued study intervention. Therefore, all participants who discontinue study intervention prior to completion of the protocol-specified treatment period regimen will still continue to participate in the study as specified in Section 1.3 and Section 8.11.3.

Participants may discontinue study intervention at any time for any reason or be dropped from the study intervention at the discretion of the investigator should any untoward effect occur. In addition, a participant may be discontinued from study intervention by the investigator or the Sponsor if study intervention is inappropriate, the study plan is violated, or for administrative and/or other safety reasons. Specific details regarding procedures to be performed at study intervention discontinuation are provided in Section 8.1.9.

A participant must be discontinued from study intervention, but continue to be monitored in the study for any of the following reasons:

- The participant or participant's legally acceptable representative requests to discontinue study intervention.
- The participant interrupts study intervention administration for more than 12 weeks without Sponsor Approval.
- The participant does not start SBRT for any reason.

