- The participant's treatment assignment has been intentionally unblinded by the investigator, MSD subsidiary, or through the emergency unblinding call center. Note: if a participant's treatment is unintentionally unblinded, the participant is not required to discontinue treatment.

- Any prolonged interruption of study intervention beyond the permitted periods, for irAE management or other allowed dose interruptions, as noted in Section 6.6, require Sponsor consultation prior to restarting treatment. If treatment will not be restarted, the participant will continue to be monitored in the study and the reason for discontinuation of study intervention will be recorded in the medical record.
- The participant has a medical condition or personal circumstance which, in the opinion of the investigator and/or Sponsor, places the participant at unnecessary risk from continued administration of study intervention.
- Pathological recurrence of disease or radiographic recurrence of disease outlined in Section 8.2.1.3. If the radiographic recurrence is biopsied and the pathology is negative, the patient may continue treatment until pathological or radiographic confirmation of recurrence by repeat imaging or biopsy.
- The participant has a confirmed positive serum pregnancy test.
- Completion of 17 doses (approximately 1 year) of pembrolizumab/placebo.
- Prohibited concomitant therapy or vaccinations as defined in Section 6.5 are administered during the study.
- Recurrent Grade 2, Grade 3, or Grade 4 pneumonitis of any cause and Grade 3 colitis.
- Any progression or recurrence of any malignancy, or any occurrence of another malignancy that requires active treatment.
- Any study intervention-related toxicity specified as a reason for permanent discontinuation as defined in the guidelines for dose modification due to AEs in Section 6.6.

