7.2 Participant Withdrawal From the Study

A participant must be withdrawn from the study if the participant or participant's legally acceptable representative withdraws consent from the study.

If a participant withdraws from the study, they will no longer receive study intervention or be followed at scheduled protocol visits.

Specific details regarding procedures to be performed at the time of withdrawal from the study, as well as specific details regarding withdrawal from FBR, are outlined in Section 8.1.9. The procedures to be performed should a participant repeatedly fail to return for scheduled visits and/or if the study site is unable to contact the participant are outlined in Section 7.3.

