8.11.4.2 Follow-up Visits

Participants who discontinue study intervention for a reason other than disease recurrence will move into the Follow-up Phase and should be assessed every 16 weeks to monitor disease status for the first 3 years, and then every 6 months thereafter. Every effort should be made to collect information regarding disease status until disease recurrence, death, or the end of the study. Information regarding poststudy anticancer treatment will be collected if new treatment is initiated. Images will continue to be obtained after the start of the new anticancer therapy if recurrence has not been documented or verified by BICR.

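### Section 6.5 says participants who need a prohibited treatment should leave the study, while Section 7.1 keeps the same participants under follow-up

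*Combined protocol and SAP*

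**What the plan says.** **Section 6.5.** The opening paragraph speaks of study treatment only: where a prohibited medication is clinically indicated, "discontinuation from study therapy or vaccination may be required". The list that follows is introduced by "Participants are prohibited from receiving the following concomitant therapy or vaccination during the course of the study". It covers systemic anticancer therapy, other immunotherapy, other investigational agents, radiation outside the protocol, live vaccines and glucocorticoids beyond the stated exceptions. After the list, the section says that participants who, in the investigator's assessment, "require the use of any of the aforementioned treatments for clinical management should be removed from the study".

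**Section 7.1.** It first states that stopping study intervention is not the same as withdrawing from the study. Its list of reasons opens with "A participant must be discontinued from study intervention, but continue to be monitored in the study for any of the following reasons", and one entry reads "Prohibited concomitant therapy or vaccinations as defined in Section 6.5 are administered during the study". It then asks that such participants complete all visits and procedures in the Schedule of Activities.

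**Section 7.2.** The reason given for withdrawal is consent: "A participant must be withdrawn from the study if the participant or participant's legally acceptable representative withdraws consent from the study". Withdrawn participants are no longer followed at scheduled visits.

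**Section 4.1.** For survival, "All participants will be followed by telephone for OS until death, withdrawal of consent, or the end of the study".

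**Section 8.11.4.2.** For disease status, "Images will continue to be obtained after the start of the new anticancer therapy if recurrence has not been documented or verified by BICR".

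**The concern.** A site reading Section 6.5 is told to take the participant out of the study. The same site reading Section 7.1 is told to keep the participant in it. Loose wording does not explain the difference, because Section 7.1 itself separates stopping treatment from leaving the study.

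The consequence is statistical. Efficacy is analysed in all randomized participants (Section 9.5.1). Without a documented death, OS is censored at the date last known alive (Section 9.6.1.2). Without an EFS event, EFS is censored at the last disease assessment (Section 9.6.1.1, Table 7). Removal at the point where anticancer therapy is needed would censor participants whose prognosis may already have changed. The list also contains live vaccines and some steroid use, so a literal reading reaches participants without recurrence too.

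For safety, Section 8.4.1 does not oblige investigators to seek events actively in former participants, so early removal could shorten active SAE collection.

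**Working it through.** No figure in the plan can be reproduced here. The check compares the text and then does one piece of date arithmetic.

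**1. Do the two rules cover the same people?** The triggers differ. Section 6.5 applies when a treatment is required, Section 7.1 when it is administered. A participant who needs a listed treatment but has not received it meets only the Section 6.5 sentence. Once it is given, both rules apply, and Section 7.1 names Section 6.5 as the source of its list.

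**2. When does the Section 6.5 rule apply?** The prohibition runs for the course of the study, not only the dosing period. Read literally, it reaches anticancer therapy started during follow-up.

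**3. Which reading does the rest of the plan need?**
- Section 1.3, survival status row: survival contact applies after investigator-determined recurrence or the start of new anticancer treatment.
- Sections 4.1 and 8.11.4.2: imaging goes on after new anticancer therapy if recurrence has not been documented or centrally verified.
- Section 8.2.1.4: a participant whose recurrence is not centrally verified stays on study.
- Table 7: a recurrence or death after new anticancer treatment counts as an EFS event on its own date. That needs follow-up past that treatment.
- Section 9.4.1.3: time to recurrence or progression on the next line of therapy cannot be observed if participants leave when that therapy starts.

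All five need continued follow-up. Section 4.1 gives imaging further stopping reasons (pregnancy, loss to follow-up, early study termination), but prohibited treatment is not among them.

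**4. How much SAE collection was still open?**
- Inputs: the memo of 29-AUG-2024 stopping treatment (Section 6.1), taken as the latest possible last dose (an assumption), and the date of 11-OCT-2024 printed on the protocol's pages.
- General SAE window (Section 8.4.1): 90 days after cessation, or 30 days if new anticancer therapy starts, whichever is earlier. Germany lists 120 days (Section 10.7.3).
- Elapsed time: 29-AUG to 28-SEP is 30 days and 28-SEP to 11-OCT is 13 days, so 30 + 13 = 43 days.
- 30-day window: ended 28-SEP-2024, before 11-OCT-2024, so nothing remained.
- 90-day window: ends 27-NOV-2024, and 90 − 43 = 47 days remained at most.
- 120-day window (Germany): ends 27-DEC-2024, and 120 − 43 = 77 days remained at most. Section 10.7.3 does not say whether the 30-day shortening also applies there.

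The 47 days therefore concern triggers other than new anticancer therapy, such as a live vaccine or a non-excepted steroid.

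**5. Can the effect on EFS or OS be sized?** No. The documents give no count of participants who received prohibited treatment or were removed because of it. Any shift in a hazard ratio would rest wholly on assumed inputs, so none is offered.

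**The case against.** The best reply is that the plan already settles the matter. Section 7 is the dedicated section and says must, where Section 6.5 says should. The opening of Section 6.5 concerns study therapy, and the follow-up rules speak directly to participants who start new anticancer therapy. The safety visit is due before such therapy starts if that comes first (Section 8.11.4.1). Adverse events present at withdrawal are still followed (Section 8.1.9), and SAEs considered related to study intervention must be reported at any time (Section 8.4.1). Treatment and efficacy follow-up have stopped, and Amendment 08 keeps the Section 7.1 text for reference only.

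Most of this stands. It supports continued follow-up as the likely intent, limits the safety loss and keeps the point minor. It does not remove the sentence, which remains in Section 6.5 without a for-reference label. Data up to the interim cutoff were gathered in a study whose current text still carries both rules.

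Three stronger readings are tempting but not supported:
- *That participants were lost and the interim result was biased.* No passage reports a removal for this reason or an effect on that analysis.
- *That the protocol ends all follow-up only for death, withdrawn consent or end of study.* Section 4.1 says this of OS telephone contact only. Imaging has other stopping reasons, and Section 7.2 does not say that consent is the sole ground for leaving.
- *That 47 or 77 days of SAE collection were at risk for everyone affected.* With new anticancer therapy, the general window had already closed.

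**Conclusion.** The sentence in Section 6.5 is wrong as written. It contradicts Section 7.1 on study follow-up for overlapping participants and does not fit the survival contact, imaging and EFS rules. That continued follow-up was intended is an inference, but a well-supported one.

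Severity is minor. The effect on EFS and OS is unknown, and the documents contain no evidence of harm. What remains is the completeness of data up to 11-JUN-2024 and a short residual safety window: at most 47 days generally at 11-OCT-2024, or 77 in Germany, assuming no dose after 29-AUG-2024 and subject to the limits shown above.

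**What to change.** Reconcile the Section 6.5 sentence with Sections 7.1 and 7.2 on one question: whether study follow-up and AE/SAE reporting continue when a prohibited treatment is needed or given. The answer should be consistent with the intention-to-treat population and Table 7, and should cover both triggers. What happens to study treatment in these cases must also read the same in both sections; no position is taken on that or on any clinical rule.

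In the report, beside the discontinuation reasons already planned in Section 9.6.4, give by arm the number of participants whose follow-up or AE/SAE window was ended under Section 6.5. For efficacy, count up to 11-JUN-2024. A count of zero would close the question.

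The cost is one sentence and one tabulation from data already held. No new data collection is needed.
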